3.3. Design of the clinical investigation

The multicenter, randomized clinical investigation is prospective, and will have a total duration of 8 weeks.

After enrollment, subjects will be randomized and assigned to two experimental groups:

- **Group A** which, alongside physiotherapy (eccentric strengthening protocol) will receive MD-Tissue Collagen Medical Device.
- **Group B** which, will implement only physiotherapy (eccentric strengthening protocol).

Variables will be assessed at baseline (T0 time), after 1 week (T1w), after 2 weeks (T2w), after 3 weeks (T3w), or at the end of injection treatment, and after 6 weeks after enrollment (T6w/FU). Further evaluation will be carried out after 2 weeks, or after 8 weeks (T8w/FU) from the start of the clinical investigation.

After enrollment, subjects in both groups will begin a 6-week physiotherapy course (eccentric strengthening protocol). Each session will consist of Achilles tendon stretching exercises. See § 3.12.

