3.9.2 Visiting Plan

T0 BASAL: Enrollment

During the daily clinical activity, the investigators participating in the study will select subjects with achilles tendinopathy through the criteria given in section 3.16 and identify those meeting the inclusion and exclusion criteria. After fully explaining the purposes, aims and procedures in the study investigation plan, the subject will be offered participation in the study. Finally, the selected subject will be asked to view the information form and date and sign the Informed Consent

The subject according to the randomization list will be assigned to Group A or Group B.

We will then proceed with the objective examination and collection of the information required by the appropriately prepared Electronic Data Collection Form.

It will be followed by:

- assessment of VISA-A score
- assessment of pain according to the VAS scale
- administration of the SF-12 quality of life test.

Previous or ongoing drug treatments of any kind will be documented.

In order to monitor the consumption of analgesic used during the clinical investigation in case of pain onset (paracetamol 1000 mg), a clinical diary will be given to the subject in which to indicate the day and dose of medication used.

The enrolled subject will be given a complex alphanumeric identification code consisting of the progressive enrollment number followed by an alphanumeric code generated through Random Sequence Generator at www.random.org.

All enrolled subjects will be trained to practice physiotherapy for the 6 weeks in the clinical study plan. Subjects belonging to Group A will be administered MD-Tissue.

T1 week:

This visit will consist of an evaluation regarding the tolerability of the administered product. During this week, the subject will have received the first two infiltrations stipulated in the clinical investigation plan. It will be verified that the clinical diary regarding analgesic consumption used has been properly completed and that the physiotherapy course is proceeding according to the clinical investigation plan.

T2 weeks:

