3.14.1. Secondaries End Points

- Evaluation of VISA-A score at time T3w and T6w/FU compared to time T0
- Assessment of the VAS score at time T3w, T6w/FU and T8w/FU compared to time T0
- Evaluation of the SF12 questionnaire at time T3w, T6w/FU, and T8w/FU compared to time T0.
- Evaluation of the fraction of subjects in each group achieving Minimal Clinical Disease (MCD) considering that the MCD of the VISA-A questionnaire is 18.5 (90% MCD).
- Assessment of analgesic drug unit consumption based on clinical diary at time T3w, T6w/FU and time T8w/FU (paracetamol 1000 mg. will be used as "rescue dose" in case of onset/recurrence of pain).
- Evaluation of the fraction of subjects in each group who drop out early in relation to Adverse Events (AE/SAE/SUSAR).

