4. STATISTICS

4.14. Sample size

A one-covariance analysis for two arms of 28 subjects each, in which the covariate of interest differs by 12 units in its mean value between the two arms (compared with a null hypothesis of no difference), with a common standard deviation assumed to be 15 units, and an R^2 value assumed to be 0.2 has a

power of 90.75% in discriminating the established difference between mean values, using an F-test at a significance level of 0.05.

Assuming dropout patients to be 20% of the total, the inflated sample size of the protocol becomes 36 patients per arm.

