4.15. Plan of statistical analysis

The primary endpoint will be evaluated by Ancova, as described in the numerosity calculation.

Secondary endpoints will be assessed as follows: 1) the VISA-A score at time T3s and T6s/FU compared with time T0 with Anova at repeated measures between group and within group; 2) the VAS at time T3s, T6s/FU and T8s/FU compared with time T0 with Anova at repeated measures between group and within group; 3) the SF12 questionnaire at time T3s, T6s/FU and T8s/FU compared with time T0 with Anova at repeated measures or Friedman's test; 4) the fraction of subjects in each group reaching Minimal Clinical Disease (MCD) considering that the MCD of the VISA-A questionnaire is 18.5 (90% MCD) with Fisher's exact test; 5) the units of analgesic drug consumed according to the clinical diary at time T3s, T6s/FUs and time T8s/FUs (paracetamol 1000 mg will be used as "rescue dose" in case of pain onset/recrudescence) with Friedman's exact test; 6) the fraction of subjects in each group who drop out of the investigation early in relation to Adverse Events (AE/SAE/SUSAR) with Fisher's exact test.

Statistical significance will be assumed for $p < 0.05$, unless corrected for multiple testing.

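### The secondary analgesic endpoint tests raw diary units over time with no counting window defined and no scaling for its length, so unchanged use can be declared a significant change.

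*Protocol*

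**What the plan says.** In the Protocol, the secondary end points in section 3.14 include "Assessment of analgesic drug unit consumption based on clinical diary at time T3w, T6w/FU and time T8w/FU". Section 4.15, item 5, takes "the units of analgesic drug consumed according to the clinical diary at time T3s, T6s/FUs and time T8s/FUs" as the quantity to be analysed and ends "in case of pain onset/recrudescence) with Friedman's exact test". The combined protocol and SAP repeats both statements. No other analysis of this endpoint is named.

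The time points come from section 3.3. The first endpoint visit is "after 3 weeks (T3w), or at the end of injection treatment", the second is six weeks after enrolment, and the last is described so: "Further evaluation will be carried out after 2 weeks, or after 8 weeks (T8w/FU) from the start of the clinical investigation". Under section 3.9.2, at T0, "a clinical diary will be given to the subject in which to indicate the day and dose of medication used".

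Neither document states the period that each of the three counts covers, and neither converts units to a daily or weekly rate.

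**The concern.** Friedman's test ranks each subject's three values against one another and asks whether the ranks differ systematically between time points. It answers a question about analgesic use only if the three values cover equal exposure. If they do not, a subject whose weekly intake never changes still has unequal counts, and the test responds to the calendar rather than to the patient.

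The trial's stated purpose includes pain reduction, and rescue use is a natural supporting measure. A significant change over time produced by the visit spacing could be reported as a finding. The exposure problem falls on the only analysis the plan names for this endpoint.

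**Working it through.** **The plan's own figure.** No power or error figure is given for this endpoint. The only one in the documents is the primary power of 90.75% in section 4.14, "using an F-test at a significance level of 0.05". Residual SD = 15 × √(1 − 0.2) = 13.42. Noncentrality = (28/2) × (12/13.42)² = 11.2. With 1 and 53 degrees of freedom the power is 90.75%, so it reproduces. The 28 evaluable subjects per arm are used below.

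**Inputs from the documents.** Visits at weeks 0, 3, 6 and 8 (section 3.3); diary issued at T0 (3.9.2); raw units and Friedman's test (4.15); significance at p < 0.05 (4.15).

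**Implied windows.**
- Since the previous endpoint visit: 3 − 0 = 3, 6 − 3 = 3 and 8 − 6 = 2 weeks. At a constant rate the last count is 2/3 of the others, that is 33% lower.
- Cumulative from T0: 3, 6 and 8 weeks, so the count can never fall.

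**Strictly constant use, by hand.** Counts in the ratio 3:3:2 give every subject ranks 2.5, 2.5 and 1. With n = 28 the rank sums are 70, 70 and 28.
- Sum of squared rank sums = 4,900 + 4,900 + 784 = 10,584.
- Value expected under no difference = 28² × 3 × 4²/4 = 9,408.
- Tie-corrected denominator = 28 × (6.25 + 6.25 + 1) − 28 × 3 × 4²/4 = 378 − 336 = 42.
- Statistic = 2 × (10,584 − 9,408)/42 = 56 on 2 degrees of freedom, p = 7 × 10⁻¹³.

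**As-needed use, by simulation.** The rate of use, its spread between subjects and the share of never-users are not in the documents, so they are assumptions, shown as a range. Each subject has a constant weekly rate and Poisson counts. The rate is the same for all, or varies between subjects (gamma, shape 1), or varies with 30% never-users. There were 4,000 trials per cell, with the tie-corrected Friedman test against chi-square at 0.05. False-positive rates with n = 28 and windows of 3, 3 and 2 weeks:

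| Units per week | Same rate | Variable rate | Variable, 30% never-users | Variable, as units per week |
|---|---|---|---|---|
| 0.25 | 17.7% | 16.5% | 12.1% | 5.8% |
| 0.5 | 31.0% | 27.2% | 19.6% | 5.1% |
| 1 | 54.5% | 47.4% | 33.7% | 4.6% |
| 2 | 85.2% | 75.0% | 56.8% | 4.8% |
| 3 | 96.2% | 88.4% | 73.0% | 5.0% |
| 5 | 99.7% | 97.6% | 87.7% | 4.4% |

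Cumulative counts reject in 100% of trials at every rate tried.

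**Controls.** Equal two-week windows give 4.3% to 6.0%. Units per week over the 3/3/2 windows give 4.4% to 5.8% at n = 28 or 36, and at most 6.8% at n = 56 or 72. A rank-sum comparison of two arms of 28 within the same two-week window, at a mean of 2 units per week and no true difference, rejects in 4.75%.

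**The case against.** **The windows are inferred.** This is correct. The documents name time points, not counting periods. The diary form is Annex G, which is not among the documents reviewed and may set a period. Table 1 also schedules a diary evaluation at T1 and T2, so counting since the last evaluation would give 1, 3 and 2 weeks. That does not rescue the test: with variable rates and n = 28, this reading rejects in 54% to 100% of trials under constant use. A weekly rate or equal look-back periods would be safe, but the plan states neither.

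**Significance is not certain.** This also stands. Paracetamol is taken as needed, so low use and many zeros are plausible. At 0.25 to 1 unit per week the error is about 12% to 55%, not near 100%.

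**A reader might infer that the test would show analgesic use falling, and so support the device.** The documents do not support that. Friedman's test gives no direction. At constant use, 3/3/2 windows make the last count lowest, cumulative counts rise, and 1/3/2 windows make the first count lowest. Both arms share the schedule, so the artefact cannot by itself favour Group A, and a comparison of the arms within one window keeps its level. The plan, however, names no such comparison for this endpoint.

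**A reader might also infer that early leavers would pass as low users.** This is unquantified and mostly limited to exits after T6, because Friedman's test needs all three values and a subject who leaves earlier drops out of it.

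**Conclusion.** The point holds as a defect in one secondary analysis. Item 5 tests raw units over time with the counting window undefined, and each of the readings examined gives unequal exposure. With constant use and 28 subjects in one arm, the since-last-endpoint-visit reading rejects in about 12% to 55% of trials at 0.25 to 1 unit per week and in about 57% to over 99% at 2 or more. The cumulative reading rejects in 100%. The nominal level is 5%.

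The size rests on assumed usage rates and on windows inferred from the visit schedule. That the error exceeds 5% does not depend on the particular rate: it did so in every scenario tried on raw units. The primary ANCOVA and the sample size are unaffected. The change should be made before the data are analysed, but it is not a threat to the trial's main conclusion.

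**What to change.** In sections 3.14 and 4.15, item 5, of both documents, define three counting windows, T0–T3, T3–T6 and T6–T8. State the endpoint as analgesic units per week in each: units recorded in the window, divided by the diary days observed in that window, times 7. Use this rate in whatever test is applied, including any comparison of Group A with Group B. A subject who leaves during a window then contributes a rate over the days observed.

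The cost is wording only. The diary already records the day and dose of each use, so no new data, visit or form is needed.

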	Enrollment	1°-2° infiltration	3°-4° infiltration	5°-6° infiltration	Physiotherapy termination	End of clinical Investigation.
Clinical and ultrasonographic diagnosis of Achilles tendon pathology	X					
Evaluation of Inclusion criteria	X					
Signing of informed consent	X					

Signature of Consent to the processing of personal data	X					
Collection of socio-demographic data	X					
Medical history collection	X					
Evaluation VISA-A score	X			X	X	X
Evaluation VAS	X			X	X	X
SF12 questionnaire administration	X			X	X	X
Infiltrative treatment		X	X	X		
Physiotherapy		X	X	X	X	
Clinical diary evaluation	X	X	X	X	X	X
Evaluation of concomitant pathologies		X	X	X	X	X
Adverse Event Evaluation (AE/SAE)		X	X	X	X	X

Tab.1 Data collection during the Study

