3.15. Early abandonment of the clinical study

Subjects may leave the clinical study for the following reasons:

- a. at their own request (even without a reason);
- b. at the discretion of the investigator.
- c. if they incur an Adverse Event.

Subjects who drop out of the clinical study before its completion will undergo a final evaluation similar to the subjects who completed it, unless the subject expressly declines.

The reason for abandonment will be reported on the Data Collection Form.

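### Analgesic use is assigned only to Friedman's test, which has no group term, so this secondary endpoint has no Group A versus Group B comparison; for SF-12 that comparison is not stated

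*Protocol*

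**What the plan says.** The Protocol and the Combined protocol and SAP have the same text on this point.

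- **Endpoint** (section 3.14.1, Secondaries End Points): "Assessment of analgesic drug unit consumption based on clinical diary at time T3w, T6w/FU and time T8w/FU". No comparison is named, and the period that each count covers is not given.
- **Analysis of analgesic units** (section 4.15, item 5): "in case of pain onset/recrudescence) with Friedman's exact test". This is the only method named.
- **Analysis of SF-12** (section 4.15, item 3): "with Anova at repeated measures or Friedman's test". No rule for choosing is given.
- **Analysis of VISA-A and VAS** (section 4.15, items 1 and 2), for contrast: "with Anova at repeated measures between group and within group".
- **Items 4 and 6** of section 4.15 compare fractions of subjects in each group with Fisher's exact test.
- **Data source** (section 3.9.2): the subject keeps a diary "in which to indicate the day and dose of medication used". The row "Clinical diary evaluation" in Table 1 is marked at every time point. The visit text says that the diary is handed out at T0, checked for completeness at T1 and T2, and used to assess consumption at T3, T6 and T8.
- **Leavers** (section 3.15) have a final evaluation "unless the subject expressly declines".

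**The concern.** The trial is meant to show what the device adds to physiotherapy, in two independent arms randomised 1:1. Every secondary analysis therefore needs a term or test that compares the arms. Items 1, 2, 4 and 6 refer to the groups. Item 5 does not, and the one test that it names cannot carry a group factor.

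As written, the endpoint asks whether analgesic use changes over the visits, not whether the device reduces it. A significant p-value could come from a fall common to both arms, or from counting over intervals of unequal length, and could then be reported as a benefit of the device. A real saving that is steady over time would be missed.

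**Working it through.** **1. The plan's own figure, to fix the scope.** The only power figure in the documents is for the primary ANCOVA (section 4.14): 28 per arm, difference 12, SD 15, R² 0.2, alpha 0.05.

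- Residual variance = 15² × (1 − 0.2) = 180, so the residual SD = 13.42.
- Noncentrality = (28/2) × 12²/180 = 11.2, with 1 and 53 degrees of freedom.
- Power = 0.9075, which matches the stated 90.75%.

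This calculation does not involve analgesic use or SF-12, so nothing below alters it.

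**2. What Friedman's test can see (no assumptions).** With n subjects and k = 3 visits, the statistic is Q = 12/[nk(k+1)] × ΣRⱼ² − 3n(k+1), apart from the correction for ties. Rⱼ is the sum over subjects of the within-subject rank at visit j. The arm appears nowhere.

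- A subject with 4, 2 and 1 units has ranks 3, 2, 1.
- Add 10 units at each visit (14, 12, 11): the ranks are still 3, 2, 1.
- Halve the use (2, 1, 0.5): the ranks are still 3, 2, 1.

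A constant shift in one arm therefore leaves Q unchanged. Generated data confirm this. Adding 20 units to every Group A value gave Q = 2.038 and p = 0.361 before and after. Adding 10 units in another data set gave p = 0.742 both times. The p-values themselves carry no meaning; the point is that they do not move. An exact version of the test uses the same ranks, so it does not help.

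**3. Illustration of size (assumed inputs).** The documents give no expected use. Assumed: Poisson counts with gamma variation between subjects (shape 0.5 to 4), 28 per arm, Group B using 0.1 to 3 units per week, and three equal periods totalling 8 weeks.

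*(a) Group A uses half of Group B at every visit.* At 1 unit per week:

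| Gamma shape | Friedman rejects | Rank-sum, A versus B, rejects |
|---|---|---|
| 0.5 | 5.2% | 27.1% |
| 1 | 5.1% | 52.8% |
| 2 | 4.2% | 79.4% |
| 4 | 4.6% | 95.8% |

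Over 0.1–3 units per week, Friedman stays at about 4–6%, its nominal error rate. The rank-sum test ranges over about 18–99%.

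*(b) Both arms fall equally* (multipliers 0.95, 0.75, 0.625; no A–B difference). Pooled Friedman rejects in about 11–12% of trials at 0.1 units per week and in 38–99% at 0.5–3. If the test is run in each arm separately, one arm is significant and the other not in about 14–15% at 0.1 and 28–48% at 0.5–3.

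*(c) Unequal counting periods, constant use, no device effect.* T0–T3, T3–T6 and T6–T8 last 3, 3 and 2 weeks. Friedman rejects in 14–99.9% on raw interval totals, in 100% on cumulative totals, and in 4.6–6.5% on units per week. The text allows any of these readings.

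**4. SF-12, by comparing the items.** Repeated-measures ANOVA can include a group factor; Friedman cannot. Items 1 and 2 say that the ANOVA is both between and within groups, and item 3 leaves this out. So the A versus B comparison is absent if Friedman is chosen, and unstated if ANOVA is chosen.

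**The case against.** **The name may be a slip for Fisher's exact test**, which stands in items 4 and 6. That is possible, but nothing in the documents shows it. Fisher's test compares fractions and does not suit a count of units, so item 5 needs correcting on either reading.

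**A group comparison is implied.** That argument has some force for SF-12 under ANOVA, where a group factor is natural. A reader might infer that SF-12 has no between-group analysis at all. The documents do not support that: one of the two permitted methods can supply it, and what is missing is the statement. For analgesic use the argument fails, because the only named test has no place for a group.

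**Friedman would still respond to a device effect.** It can, if the effect changes over the visits. With Group A at 0.9, 0.5 and 0.25 of Group B, it rejects in about 14% of trials at 0.1 units per week and in 41–98% at 0.5–3. So it would be wrong to infer that the test is blind to every device effect. But the shared fall in (b) gives similar rejection rates with no device effect, so the result cannot be attributed to the device.

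**The percentages reflect the chosen inputs.** This stands. The ranges are wide because expected use is unknown. Only the invariance in step 2 is free of assumptions, and it is enough to establish the defect.

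**It is only a secondary endpoint.** This also stands and limits the severity.

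**Conclusion.** The point holds. Item 5 of section 4.15 gives analgesic use no test of Group A against Group B, and no other section supplies one. A significant Friedman result would show change over visits, which could be a fall shared by both arms or an effect of the 3-, 3- and 2-week periods. SF-12 certainly has the same gap if Friedman is chosen; under ANOVA the comparison is not stated.

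The invariance result rests on no assumption. The rejection rates (about 4–6% for Friedman against 18–99% for a rank-sum test when Group A uses half; about 11–99% for Friedman under a shared fall) rest on the assumed count model and 0.1–3 units per week.

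A reader might infer that the trial's main conclusion is at risk. It is not: the primary ANCOVA compares the arms, and its 90.75% power reproduces. This should be fixed before the analysis, but it is limited to one secondary endpoint and, in part, SF-12.

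**What to change.** **Item 5 (analgesic use).** Replace Friedman's test with one prespecified comparison of Group A with Group B on analgesic units per observed week from T0. Use a rank-based two-sample test that allows ties, with a matching effect estimate and 95% CI. Brunner-Munzel is one suitable choice among several: it gives the probability that a Group A subject uses less than a Group B subject, with ties counted half. Define the period that each count covers, and present the T3, T6 and T8 figures descriptively as units per week.

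**Item 3 (SF-12).** State that the ANOVA is between and within groups, as in items 1 and 2. If a non-parametric fallback is kept, make it a between-group test on change from T0 with a stated rule for choosing it, not Friedman's test.

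**Leavers.** The sample size allows for them ("Assuming dropout patients to be 20% of the total"), and some may decline the final evaluation. State whether their partial diaries count and when their observed time ends.

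**Cost.** The change is to the wording of section 4.15; the diary already records day and dose. If leavers' partial diaries are to count, a diary count must also be entered at T1 and T2. That is a new data-entry step, because section 3.9.2 now asks only for a check of completeness at those visits. The sample size does not change.

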3.5. Participant population

A total of 72 subjects with achilles tendinopathy will be enrolled. The recruitment phase will be closed no sooner than the number of subjects in the clinical investigation plan has been reached.

Only subjects will be included in the two experimental groups:

- belonging to the departments of the experimental centers;
- who meet the inclusion criteria and have no exclusion criteria.

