#### 4.15. Plan of statistical analysis

The primary endpoint will be evaluated by Ancova, as described in the numerosity calculation.

Secondary endpoints will be assessed as follows: 1) the VISA-A score at time T3s and T6s/FU compared with time T0 with Anova at repeated measures between group and within group; 2) the VAS at time T3s, T6s/FU and T8s/FU compared with time T0 with Anova at repeated measures between group and within group; 3) the SF12 questionnaire at time T3s, T6s/FU and T8s/FU compared with time T0 with Anova at repeated measures or Friedman's test; 4) the fraction of subjects in each group reaching Minimal Clinical Disease (MCD) considering that the MCD of the VISA-A questionnaire is 18.5 (90% MCD) with Fisher's exact test; 5) the units of analgesic drug consumed according to the clinical diary at time T3s, T6s/FUs and time T8s/FUs (paracetamol 1000 mg will be used as "rescue dose" in case of pain onset/recrudescence) with Friedman's exact test; 6) the fraction of subjects in each group who drop out of the investigation early in relation to Adverse Events (AE/SAE/SUSAR) with Fisher's exact test.

Statistical significance will be assumed for  $p < 0.05$ , unless corrected for multiple testing.

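### The only planned safety analysis is dropout because of adverse events, which ignores events in subjects who stay and is insensitive unless such dropout is common in one arm and near zero in the other

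*Protocol*

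**What the plan says.** In the Protocol, the secondary end points in 3.14 include "Evaluation of the fraction of subjects in each group who drop out early in relation to Adverse Events (AE/SAE/SUSAR". Section 4.15, item 6, assigns Fisher's exact test to "the fraction of subjects in each group who drop out of the investigation early in relation to Adverse Events (AE/SAE/SUSAR". The Combined protocol and SAP has the same analysis in its 4.15: "who drop out of the investigation early in relation to Adverse Events (AE/SAE/SUSAR) with Fisher's exact test". The other five items in 4.15 cover VISA-A, VAS, SF-12, the VISA-A responder fraction and analgesic use. None of them concerns safety.

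The significance rule in 4.15 is "Statistical significance will be assumed for $p < 0.05$, unless corrected for multiple testing". It does not say whether tests are one-sided or two-sided.

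The plan collects much more safety information than item 6 uses. Section 3.9.2 and its Table 1 schedule AE evaluation at T1, T2, T3, T6 and T8, and make tolerability of the product the purpose of the T1 and T2 visits. Section 5.3 classifies AEs by seriousness and grades the non-serious ones as mild, moderate or severe. No summary, estimate or between-arm comparison of AE incidence, severity or tolerability is specified.

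On numbers, 3.5 states "A total of 72 subjects with achilles tendinopathy will be enrolled" and 4.14 states "Assuming dropout patients to be 20% of the total, the inflated sample size of the protocol becomes 36 patients per arm".

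**The concern.** There are two separate problems.

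The first is what the measure counts. It registers an AE only if the subject leaves because of it. Group A receives six injections over three weeks (3.11). A subject with a local reaction to all six who completes the study is scored the same as a subject with no reaction at all.

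The second is sensitivity. AE dropout is a small subset of AEs, and 36 per arm is few subjects for comparing rare events by an exact test. A non-significant item 6 could then be read as evidence that the injections are well tolerated, which it may be unable to support. Section 5.2 notes that no studies have evaluated the efficacy of these devices in this condition. With no AE summary specified in advance, its form would be chosen after the data are seen, in a trial that describes no blinding and whose control arm receives no injection.

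**Working it through.** **Inputs.** 72 subjects (3.5), 1:1 allocation (3.8), hence 36 per arm (4.14). Fisher's exact test at 0.05 (4.15). Assumed, because the documents are silent: a two-sided test, and the true AE-dropout rates.

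**The plan's own figures.** The stated ANCOVA power reproduces. The error SD is 15 × √(1 − 0.2) = 13.42, and the noncentrality is (28/2) × (12/13.42)² = 11.2. With 1 and 53 degrees of freedom, power is 90.75%. For dropout, 28/(1 − 0.20) = 35, against a stated 36, which is close enough. These figures concern the primary endpoint. No power or expected rate is given for item 6.

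**Smallest significant result.** With equal arms of 36 and *a* events all in one arm, the two-sided p-value is 2 × C(36,a)/C(72,a).

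- 5 v 0: 2 × 376,992/13,991,544 = 0.054
- 6 v 0: 2 × 1,947,792/156,238,908 = 0.025

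So at least 6 v 0 is needed. Each event in the other arm raises the requirement:

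| Events in the lower arm | Events needed in the higher arm | p |
|---|---|---|
| 0 | 6 | 0.025 |
| 1 | 8 (7 gives 0.055) | 0.028 |
| 2 | 9 | 0.046 |
| 3 | 11 | 0.035 |

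**Power.** This is the exact unconditional power: two independent binomial probabilities (n = 36 each), summed over all tables with p < 0.05. When one arm's rate is 0% it reduces to P(X ≥ 6), with X binomial(36, rate).

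| True AE dropout (assumed) | Power |
|---|---|
| 5% v 0% | 0.8% |
| 10% v 5% | 3.2% |
| 10% v 2% | 8.0% |
| 10% v 0% | 14.5% |
| 15% v 5% | 14.6% |
| 15% v 0% | 46% |
| 20% v 0% | 75% |
| 35% v 5% | 88% |

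For 80% power the higher arm needs about 21.5% if the other is 0%, 31.5% if it is 5%, and 40% if it is 10%.

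**What no events would show.** With 0 of 36, the upper limit of the exact two-sided 95% interval is 1 − 0.025^(1/36) = 9.7%.

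**The alternative measure.** The same Fisher test applied to the proportion with any AE, at assumed rates, has power of 34% for 20% v 5%, 47% for 30% v 10%, and 80% for 40% v 10%. It uses more of the data, but it is not reliably powered either. That favours estimation over a replacement test.

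**The case against.** A reader might combine the 20% dropout assumption with 36 per arm and infer that item 6 can almost never show a difference. If the 20% fell equally, each arm would have 0.20 × 36 = 7.2 dropouts. With at most 7 events per arm, only 6 v 0 and 7 v 0 are significant. The documents do not support that inference. The 20% in 4.14 covers all causes, is used only to inflate the sample, and is not split by arm or reason; AE is one of three reasons for leaving in 3.15. A poorly tolerated injection would make dropout unequal, which is what the endpoint is meant to detect. At 20% v 0%, an average of 10% and so half of the assumed dropout, power is 75%. At 40% v 0%, where all of it is AE-related and in one arm, power is 99.9%.

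A reader might also infer that AEs will go unreported. They will not: 3.9.2 requires every AE from consent to study end to be recorded and reported, and 5.3 requires follow-up of unresolved events. Those are obligations for individual events, however, and do not say how the arms will be summarised.

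Other objections stand in part. A one-sided test at 0.05 would need only 5 v 0 (0.0539/2 = 0.027). No section says that a non-significant item 6 will be taken as proof of tolerability. Comparing AE proportions has its own bias: Group A has injection contacts that Group B lacks, treatment is open, and injection-site events have no counterpart in Group B. These points limit how the fix should be framed. They do not rescue AE dropout as the sole safety measure.

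**Conclusion.** The concern holds. Item 6 is the only safety analysis, and it discards AEs in subjects who stay in the study. That follows from the text alone and needs no assumed rate.

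Its insensitivity is conditional. The test is weak unless AE dropout is common in one arm and near zero in the other. Power is about 15% or less when the higher arm is at 10% or below, and reaches 80% only at about 21.5% v 0%. These figures rest on 36 per arm, a two-sided test at 0.05 without multiplicity correction, and AE-dropout rates that the documents do not give. A multiplicity correction would lower the power further.

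The primary endpoint is unaffected. The plan should be changed because the present measure cannot support a statement about tolerability, and the data for a better one are already being collected.

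**What to change.** In 3.14 and 4.15 item 6, in both documents:

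- Make the safety measure the proportion of subjects with at least one AE in each arm, with the risk difference and an exact or score 95% confidence interval. Present it as estimation, not as a powered test, and state the denominator.
- Tabulate SAEs and AE severity by arm.
- Report injection-site events descriptively, for Group A only.
- Keep AE-related dropout as a count per arm with its confidence interval.
- State that a non-significant difference is not evidence of equal safety.

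The cost is a change of wording and additional tables from data already collected, with no extra subjects or visits. The downside is that open-label reporting and the extra injection contacts may raise AE ascertainment in Group A. The report should say so when interpreting the risk difference.
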